6.3. Lifestyle Restrictions

- Patients should be instructed not to donate blood or blood products during the study.
- Patients should be instructed to avoid major changes in dietary intake or physical activity during the 3 days prior to MMTT.

6.4. Screen Failures

Individuals who do not meet the criteria for participation in this study (screen failure) may not be rescreened. Retests are also not allowed, except for cases when results are not available from the original sample.

7. Treatments

7.1. Treatments Administered

This study involves a comparison of LY900014 and insulin lispro administered SC 0 to 2 minutes prior to the start of the meal for 26 weeks.

Table ITSD.2 shows the treatment regimens.

Table ITSD.2. Treatment Regimens

	Dose	Dose	Route of	Timing of
Regimen	Strength	Administration	Administration	Administration
LY900014		Individualized dosing	Subcutaneous	0 to 2 minutes before start of the meal
Insulin lispro		Individualized dosing	Subcutaneous	0 to 2 minutes before start of the meal

The investigator or his/her designee is responsible for the following:

- explaining the correct use of the IP to the patient including the importance of injection site rotation for both basal and prandial insulin
- explaining requirements for recording insulin doses and injection times to the patient
- verifying that instructions are followed properly
- maintaining accurate records of IP dispensing and collection
- at the end of the study, returning all used and unused IP to Lilly, or its designee, unless the sponsor and sites have agreed all unused medication is to be destroyed by the site, as allowed by local law

7.1.1. Packaging and Labeling

Clinical trial materials will be labeled as IP as appropriate, and according to the country's regulatory requirements. Study insulins (LY900014 and insulin lispro) will be supplied by Lilly or its representative, in accordance with current good manufacturing practices, and will be supplied with clinical trial lot numbers. Instructions for Use for the prefilled devices will be provided.

The blinded prefilled pens will contain a concentration of 100 U/mL in 3-mL cartridges of either LY900014 or insulin lispro.

During the lead-in period, 100 U/mL insulin lispro will be provided using open-label prefilled pens.

7.1.2. Medical Devices

The medical devices provided for use in the study are prefilled pens. LY900014 prefilled pens are new investigational combination products.

7.2. Method of Treatment Assignment

Patients who meet all criteria for enrollment will be randomized to double-blind treatment at Visit 8. Assignment to treatment groups will be determined by a computer-generated random sequence using an interactive web-response system (IWRS). Patients will be randomized to 1 of the 2 treatment groups in a 1:1 ratio. Stratification will be by country (China vs. Other), HbA1c stratum (≤8.5% vs. >8.5% at Visit 7), type of basal insulin during the lead-in period (glargine U-100 vs. degludec U-100), and use of metformin at study entry (yes vs. no).

The IWRS will be used to assign all IP during the study, including insulin lispro during the lead-in period. The IWRS will be used to assign prefilled pens containing double-blind IP to each patient randomized to the 2 blinded treatment groups. Site personnel will confirm that they have located the correct prefilled pens by entering a confirmation number found on the prefilled pens into the IWRS.

7.2.1. Selection and Timing of Doses

7.2.1.1. Target Glucose Values for Titration of Insulin Therapy

The overall glycemic control goals for all patients enrolled in the study are similar to those recommended by the American Association of Clinical Endocrinologists (Bailey et al. 2016). Fasting, prandial, postprandial, and bedtime glucose target values used to reach the SMBG goals and for determination of titration in insulin therapy are listed in Table ITSD.3.

Table ITSD.3. Target Glucose Values for Adjustment of Insulin Therapy

Time of Target Blood Glucose Measurement	Self-Monitored Blood Glucose (SMBG) Target (Range)	
Fasting or pre morning meal	Target: 100 mg/dL or 5.6 mmol/L	
	Range: 80 to <110 mg/dL or 4.4 to 6.1 mmol/L	
Pre midday meal	Target: 100 mg/dL or 5.6 mmol/L	
	Range: 80 to <110 mg/dL or 4.4 to 6.1 mmol/L	
Pre evening meal	Target: 100 mg/dL or 5.6 mmol/L	
	Range: 80 to <110 mg/dL or 4.4 to 6.1 mmol/L	
Pre bedtime	Range: 90 to 130 mg/dL or 5.0 to 7.2 mmol/L	
1-2 hour postprandial	Target: <140 mg/dL or 7.8 mmol/L	

Note: Every effort should be made to reach the targets while avoiding hypoglycemia.

7.2.1.2. Basal Insulin Therapy

At Visit 2, patients will be transferred to insulin glargine U-100 (Basaglar/Abasaglar or LANTUS) once daily or to degludec U-100 once daily in accordance with local regulations if the patient enters the study on any other basal insulin regimen. The initial basal insulin dose may be unit-for-unit of the prestudy basal insulin regimen or 80% of the prior basal insulin daily dose if the patient was previously treated with twice-daily NPH.

At Visit 2, patients treated with premixed insulin will be transferred to an allowed study basal insulin and to insulin lispro (see Section 7.2.1.4). Patients transitioning from regular human insulin or human insulin mixtures should be reminded about the importance of injecting insulin lispro immediately prior to meals. The total daily insulin dose will be divided between basal and bolus insulin doses at the discretion of the investigator. The initial basal insulin dose may be approximately 40% to 60% of the total daily dose. The initial prandial insulin dose may be approximately 40% to 60% of the total daily dose. The distribution for use across the 3 main meals is at the discretion of the investigator. The basal insulin dose may be influenced by other clinical circumstances and safety considerations known to the investigator; thus, the prescribed basal insulin dose during the study is determined by, and the responsibility of the investigator.

Patients should use the same study basal insulin regimen throughout the trial. The study basal insulin can be dosed at any time during the day and should be taken at approximately the same time of day throughout the course of the study.

7.2.1.3. Basal Insulin Titration

At all clinic and telephone visits during the 8-week lead-in period, basal insulin dose adjustments should be determined by the investigator in discussion with the patient based on SMBG and hypoglycemia data. Additional discussion between visits may be required to enable the patient to reach the FBG target. Patients' basal insulin should be titrated using the titration algorithm to reach the FBG target of 100 mg/dL (5.6 mmol/L).

Decreases to the basal insulin dose may be made at any time based upon the judgment of the investigator (for example, in response to hypoglycemia). Modifications in the calculation of the basal insulin dose may also be influenced by other clinical circumstances and safety considerations known to the investigator; thus, the prescribed basal insulin dose during the study is determined by, and the responsibility of, the investigator.

Every effort should be made to reach the FBG target during the lead-in period to allow enough time for prandial insulin dose adjustments during the titration period; however, basal insulin dose may be adjusted if needed to facilitate optimal prandial insulin dosing during the intensive titration period (Weeks 0 to 12) or for safety reasons. Thereafter, during the maintenance period (Weeks 12 to 26), it is expected that adjustments to basal insulin doses would be to maintain glycemic control or for safety reasons such as hypoglycemia or unacceptable hyperglycemia.

Assessments of the basal insulin dose should be made at least at weekly intervals based upon the occurrence of hypoglycemia events during the previous week (Table ITSD.4). After the hypoglycemia assessment, the median FBG value from the 3 previous corresponding FBG values can be used for basal insulin adjustment as in Table ITSD.5. Additional discussion between

visits may be required to enable the patient to reach the FBG target. The basal insulin dose may be adjusted every 3 to 4 days (twice per week) when appropriate, based on the patient's glycemic needs and SMBG levels. Investigators may use discretion and provide direction for patients to adjust the basal insulin dose.

Table ITSD.4. Basal Insulin Hypoglycemia Assessment

Hypoglycemic Events in the Previous Week	Basal Insulin Change (units)
2 or more nocturnal hypoglycemia events occur or 1 severe	Titrate the basal dose down to the previous basal
hypoglycemia event occurs at any time of the day	insulin dose (or by 10% if this is first dose)
1 nocturnal hypoglycemia event occurs	Do not increase basal insulin dose and consider
	reducing the dose if clinically indicated
	Titrate the basal insulin up based upon the median
No nocturnal events occur	FBG for the previous 3 FBG values. See
	Table ITSD.5

Abbreviation: FBG = fasting blood glucose.

Table ITSD.5. Summary of Basal Insulin Adjustments after Hypoglycemia Assessment

	When Basal Insulin ≤14 units	When Basal Insulin ≥15 units
If median FBG from the 3	Adjust the basal dose by:	Adjust the basal dose by:
previous FBG values is:		
<80 mg/dL	Decreasing dose to previous lower dose ^a	Decreasing dose to previous lower dose ^a
(<4.4 mmol/L)		
80–100 mg/dL	No adjustment	No adjustment
(4.4–5.6 mmol/L)		
101–139 mg/dL	Increasing by 1 unit	Increasing by 2 units
(5.7–7.7 mmol/L)		
140–179 mg/dL	Increasing by 2 units	Increasing by 3 units
(7.8–9.9 mmol/L)		
≥180 mg/dL	Increasing by 3 units	Increasing by 4 units
(≥10 mmol/L)		

Abbreviation: FBG = fasting blood glucose.

Sources: Adapted from Bartley et al. 2008 and Bolli et al. 2009.

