a Median SMBG value at target range OR experienced 1 unexplained hypoglycemic event (≤70 mg/dL [3.9 mmol/L]) or signs/symptoms consistent with hypoglycemia noted.

Target Range: Premeal: 80 to <110 mg/dL (4.4 to 6.1 mmol/L)

Bedtime: 90 to 130 mg/dL (5.0 to 7.2 mmol/L) 1-2 hour postprandial: <140 mg/dL (7.8 mmol/L).

Source: Adapted from Bergenstal et al. 2008.

Patients who wear their personal CGM/FGM device prior to study entry will be allowed to continue to wear their CGM/FGM device during the study. However, these patients should be instructed to perform SMBG monitoring using the study glucose meter according to the protocol. Investigators must use the SMBG levels to make treatment decisions. Patients should not start using a personal CGM/FGM device after Visit 2.

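### Table ITSD.4 gives conflicting basal insulin instructions after a severe daytime hypoglycemic event with no nocturnal event, and Table ITSD.7 has a lesser overlap

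*Protocol*

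**What the plan says.** Protocol 7.2.1.3 asks for a basal dose assessment at least weekly, based on the previous week's hypoglycemia (Table ITSD.4). After that assessment, the median of three fasting values can be used with Table ITSD.5.

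Table ITSD.4 has three rows:

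- Row 1 is triggered by "2 or more nocturnal hypoglycemia events occur or 1 severe" event, and the cell continues "hypoglycemia event occurs at any time of the day". The instruction begins "Titrate the basal dose down to the previous basal" dose, with a 10% cut if there is no earlier dose.
- Row 2 is triggered by one nocturnal event. The instruction begins "Do not increase basal insulin dose and consider" a reduction if clinically indicated.
- Row 3 is triggered when "No nocturnal events occur". The instruction is to titrate up from the median FBG, using Table ITSD.5.

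Protocol 9.4.1 defines nocturnal events as those between bedtime and waking, severe ones included.

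For prandial insulin, Protocol 7.2.1.4 gives Table ITSD.7 to patients on the pattern adjustment plan. It has one column each for a median below, at and above the target range. Footnote a to the middle (no change) column reads "Median SMBG value at target range OR experienced 1 unexplained hypoglycemic event", and also admits signs or symptoms of hypoglycemia.

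The SAP does not restate or amend these tables.

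**The concern.** A titration table should give one instruction for each patient state. Row 1 of Table ITSD.4 counts severe events at any hour, while row 3 looks only at nocturnal events. A severe event in the daytime therefore triggers row 1 without taking the patient out of row 3. Read on its own, row 3 allows a basal increase in the week after a severe event.

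What is at stake is patient safety. The protocol requires severe hypoglycemia to be reported as a serious adverse event (9.2.1), and its rate is a secondary endpoint (Section 4). Patients with one severe episode in the six months before screening may enter (exclusion 16). Protocol 7.2.1.3 also lets investigators direct patients to adjust their own basal dose, so the table may be applied away from the clinic.

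**Working it through.** The plan has no figure to reproduce on this point. The check is to list the patient states and read off every row that applies.

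**Step 1: Table ITSD.4, all combinations in the previous week**

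| Nocturnal events | Severe event | Rows met |
|---|---|---|
| 0 | no | 3 |
| 0 | yes (so daytime) | 1 and 3 |
| 1 | no | 2 |
| 1 | yes | 1 and 2 |
| 2 or more | no | 1 |
| 2 or more | yes | 1 |

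Two states meet more than one row. In the state with one nocturnal event and a severe event, row 1 requires a reduction and row 2 asks that one be considered. These differ in force but do not pull in opposite directions. The state with no nocturnal event and a severe daytime event is the real conflict.

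**Step 2: take that state through Table ITSD.5**

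| Median FBG (mg/dL) | Row 1 | Row 3, through Table ITSD.5 (basal ≤14 U / ≥15 U) | Comparison |
|---|---|---|---|
| below 80 | down | down to previous lower dose | agree |
| 80–100 | down | no adjustment | differ |
| 101–139 | down | +1 / +2 units | opposite |
| 140–179 | down | +2 / +3 units | opposite |
| 180 or more | down | +3 / +4 units | opposite |

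**Step 3: size of the gap when opposite.** The documents do not fix the previous dose, so this needs an assumption: that the last change was one Table ITSD.5 increase, of 1 to 4 units. Row 1 then takes off 1 to 4 units and row 3 adds 1 to 4. The smallest gap is 1 + 1 = 2 units and the largest is 4 + 4 = 8 units.

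**Step 4: look for a rule that decides between the rows.** The text linking the two tables allows Table ITSD.5 after the hypoglycemia assessment but does not limit it to patients outside row 1. No sentence says that rows are read from the top, or that a severe event overrides row 3.

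**Step 5: Table ITSD.7, pattern adjustment only.** Take a patient with one unexplained hypoglycemic event:

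- Median below range: decrease by 1, 2 or 3 units (by size of the mealtime dose), and no change under footnote a.
- Median in range: no change only.
- Median above range: increase by 1, 2 or 3 units, and no change under footnote a.

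Two columns apply whenever the median is out of range. The choice is between a step and no step, so the columns overlap but are not opposite. Patients who count carbohydrates do not use this table.

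**The case against.** The strongest reply is that no careful site would raise the dose. Row 1 comes first and names this very patient. The hypoglycemia assessment precedes Table ITSD.5, whose use is optional. Protocol 7.2.1.3 allows decreases at any time, for example in response to hypoglycemia, and makes the investigator responsible for the dose. The investigator also classifies each severe event.

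Much of this stands. An increase would mean disregarding row 1, and these provisions lower the practical risk. But they let the investigator depart from the algorithm without saying what the algorithm instructs, and reading from the top is sensible but not written down.

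A reader might also infer three stronger points that the documents do not support:

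- *That Tables ITSD.3 and ITSD.5 contradict each other.* Table ITSD.3 gives a fasting "Range: 80 to <110 mg/dL or 4.4 to 6.1 mmol/L", yet Table ITSD.5 starts "Increasing by 1 unit" at 101 mg/dL for the lower basal doses, so 101–109 mg/dL is in range and still raises the dose. But Table ITSD.3 also gives a fasting target of 100 mg/dL, and Protocol 7.2.1.3 says basal insulin is titrated to that target. Table ITSD.5 does so. No text holds the basal dose constant across the whole range.
- *That every overlap is an opposite instruction.* Only rows 1 and 3 of Table ITSD.4 are, and only above 100 mg/dL.
- *That differing site readings distort the HbA1c or hypoglycemia results.* No mechanism, frequency or size can be drawn from the documents. Treatment is double-blind, both arms use the same tables, and most basal adjustment is expected before randomization.

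**Conclusion.** The conflict in Table ITSD.4 is real and the table is wrong as written. For a patient with one severe daytime event and no nocturnal event in the previous week, it gives two instructions that are opposite above a median FBG of 100 mg/dL, different at 80–100 mg/dL and the same below 80 mg/dL. Table ITSD.7 has a lesser overlap, limited to pattern-adjustment patients with one unexplained event and an out-of-range median.

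The documents do not say how often either state arises, so the number of patients affected cannot be estimated. The 2-to-8-unit gap rests on the stated assumption about the previous dose. The conclusion itself rests only on reading the rows as written and on the definition of nocturnal in Protocol 9.4.1.

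It would go too far to say that the protocol directs an increase after a severe event: row 3 allows one, while row 1 points the other way. This is a patient-safety wording conflict that leaves sample size and error rates untouched.

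**What to change.** The sponsor should reconcile two places so that each patient meets one instruction:

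- **Table ITSD.4:** make the three rows mutually exclusive, or state which row prevails when more than one applies. Either also settles the smaller overlap of rows 1 and 2.
- **Table ITSD.7:** reconcile footnote a with the three columns, so that it is clear which column applies after one unexplained event when the median is out of range.

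Which instruction should prevail is a clinical decision for the sponsor's medical team, and none is proposed here. The cost is a clarification of the protocol tables and a memo to sites. Sample size and data collection do not change.

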7.2.1.4. Study Prandial Insulin Therapy

Patients treated with insulin aspart, insulin glulisine, or regular human insulin as their prestudy prandial insulin will be transferred to insulin lispro (unit for unit or decreased by 10% to 20% for regular human insulin to avoid hypoglycemia at investigator discretion) at Visit 2. Insulin lispro will be dispensed to all patients for use throughout the lead-in period.

At Visit 2, patients treated with premixed insulin will transition to 3 injections of prandial insulin with 3 main meals a day. The total daily insulin dose will be divided between basal and bolus insulin doses at the discretion of the investigator. The initial basal insulin dose may be approximately 40% to 60% of the total daily dose. The initial prandial insulin dose may be approximately 40% to 60% of the total daily dose. The initial distribution of prandial insulin

^a If there is no previous dose because this was the first assigned dose after randomization, then the basal dose should be decreased by 10% in consultation with the investigator.

may be equal (33% of total daily prandial dose prior to each meal). Otherwise, the investigator, in consultation with the patient, may alter the percentage of prandial insulin prescribed at each meal as clinically indicated, such as by the patient's history of prandial insulin administration, SMBG levels, and meal pattern. The prandial insulin dose may be adjusted if needed (for safety reasons such as hypoglycemia or unacceptable hyperglycemia) during the lead-in as clinically indicated.

Patients will be randomized (Visit 8) to either LY900014 or insulin lispro at mealtime. Patients will administer their first study prandial insulin with the next meal following the baseline MMTT. Patients should have 3 doses of prandial insulin per day and eat 3 main meals per day (morning, midday, and evening) on a regular basis. Patients may also eat a snack and cover with bolus insulin if that is their usual practice.

This study will use 2 possible plans for determining prandial insulin dosing including:

- [1] Pattern adjustment: The patient is prescribed a fixed dose or dose range of insulin for each meal. The fixed insulin dose may be individualized for each meal.
- [2] Carbohydrate counting: The patient performs carbohydrate counting for prandial insulin dosing (ICR plan) and prandial insulin dose is based upon the estimated carbohydrate content of the meal (as unit insulin per grams carbohydrate).

The patient should maintain the same prandial insulin dosing plan throughout the study. Correction factor(s) (for example, 1 unit of insulin per glucose [mg/dL or mmol/L] above target goal) may be implemented with either prandial insulin dosing plan. Adjustments in insulin dosage should also take into account conditions of stress and/or exercise and should be made individually.

At randomization (Visit 8), the starting study insulin doses may be initiated unit for unit; however, investigators may consider reducing the prandial or correction insulin doses approximately 10% to 20% based on the patient's overall glycemic status or other considerations known to the investigator in order to reduce risk of postprandial hypoglycemia.

For patients who are carbohydrate counting, the ICR and CF should be assessed and adjusted as needed, at least weekly, in order to meet the target SMBG levels described in Table ITSD.3 during the initial 12 weeks after randomization (the intensive titration period). The ICR may be adjusted every 3 to 4 days (twice per week) when appropriate, based on the patient's glycemic needs and SMBG levels. Postprandial SMBG levels from 10-point SMBG profiles should also be evaluated for optimization of prandial insulin dosing. Additional 2-hour postprandial SMBG monitoring should be considered during the days following transition to study insulin beginning at Visit 8. During the maintenance period (Weeks 12 to 26), it is expected that prandial insulin dose adjustments should be made to maintain glycemic control and for safety reasons such as hypoglycemia or unacceptable hyperglycemia; however, if SMBG targets have not been achieved, titration of prandial insulin should continue.

For patients who are using pattern adjustment, the prandial insulin dose should be assessed and adjusted as needed 1 to 2 times each week, and the CF should be assessed and adjusted weekly

as needed during the initial 12 weeks after randomization (the intensive titration period). In addition to the weekly investigator dose assessment, investigators may use discretion and encourage patients to make 1 additional prandial insulin dose adjustment per week. Prandial insulin dose adjustments for more than twice per week will not constitute a protocol violation. During the maintenance period (Weeks 12-26), prandial insulin dose adjustments should be made in order to maintain glycemic control and for safety reasons such as hypoglycemia or unacceptable hyperglycemia; however, if glycemic and SMBG targets have not been achieved, titration of prandial insulin should continue. Modifications in the calculation of the insulin dose may also be influenced by other clinical circumstances and safety considerations known to the investigator. Therefore, the prescribed prandial insulin dose is determined by, and the responsibility of, the investigator.

In the pattern adjustment plan, assessment of the prandial insulin dose includes review of the previous 3 to 7 days of SMBG levels for the corresponding meal or bedtime (Table ITSD.6). For example, if assessing the need to adjust the fasting (pre morning meal) prandial insulin dose, review the preceding 3 to 7 pre midday meal SMBG levels.

Table ITSD.6. Prandial Insulin Doses and Corresponding Self Monitored Blood Glucose Values Pattern Adjustment Plan

Prandial Insulin Dose Assessed	Corresponding SMBG Values for Review
Fasting or morning premeal	3-7 previous midday premeal SMBG values
Midday premeal	3-7 previous evening premeal SMBG values
Evening premeal	3-7 previous bedtime SMBG values

Abbreviation: SMBG = self-monitored blood glucose.

The median value from premeal glucose readings from the 3 to 7 previous days is chosen as the "adjustment value" and the change in dose (either increase or decrease) is based upon this value (Table ITSD.7).

Table ITSD.7. LY900014 or Insulin Lispro Adjustment Algorithm Pattern Adjustment Plan

If Meal Time Dose of Insulin Lispro is:	Median SMBG Value Below Target Range	Median SMBG Value at Target Range ^a	Median SMBG Value Above Target Range
≤10 units	Decrease by 1 unit	No change	Increase by 1 unit
11–19 units	Decrease by 2 units	No change	Increase by 2 units
≥20 units	Decrease by 3 units	No change	Increase by 3 units

Abbreviation: SMBG = self-monitored blood glucose.

a Median SMBG value at target range OR experienced 1 unexplained hypoglycemic event (≤70 mg/dL [3.9 mmol/L]) or signs/symptoms consistent with hypoglycemia noted.

Target Range: Premeal: 80 to <110 mg/dL (4.4 to 6.1 mmol/L)

Bedtime: 90 to 130 mg/dL (5.0 to 7.2 mmol/L) 1-2 hour postprandial: <140 mg/dL (7.8 mmol/L).

Source: Adapted from Bergenstal et al. 2008.

Patients who wear their personal CGM/FGM device prior to study entry will be allowed to continue to wear their CGM/FGM device during the study. However, these patients should be instructed to perform SMBG monitoring using the study glucose meter according to the protocol. Investigators must use the SMBG levels to make treatment decisions. Patients should not start using a personal CGM/FGM device after Visit 2.

